In this evaluation, we aim to test the impact of Tips by Text compared to business as usual using a two-arm randomised controlled trial (RCT). The text messages are designed to provide parents of children in reception year (4-5 years old) with information and strategies to help their children's development outside of the school environment. Three types of messages are sent every week including during the school holidays which parents can tailor to work with their children. The three types of messages are: "FACT" texts, designed to inform and motivate parents by highlighting the importance of a particular skill or set of skills; "TIP" texts, designed to minimise the cognitive, emotional, and time burdens of engaged parenting by include short, simple, and highly-specific activities for parents to do with their children that build on existing family routines; and "GROWTH" texts, which provide encouragement, reinforcement, and extend the TIP texts.

Ultimately 109 schools from the North-East of England were recruited to participate in the trial. Parents of reception children in these schools were randomly allocated to one of two groups; (1) the control group (no text messages) or (2) the treatment group who receive three text messages per week. It was intended that parents allocated to the treatment group would receive text messages from early November 2019 to late July 2020 (9 months in total). In practice, the period of text message delivery has been extended to end October 2020 as a result of the Covid-19 crisis so the children will have moved into Year 1 and therefore be aged 5-6 by the post-test (please see updates to the trial protocol for further details).

The primary analysis will examine the impact of Tips by Text on children's literacy outcomes using the York Assessment for Reading Comprehension (YARC) and then secondary analysis will explore socio-emotional outcomes using the Strengths and Difficulties Questionnaire.

The primary research question is therefore:

RQ1. Does the Tips by Text intervention improve Reception children's literacy outcomes?

The secondary research questions are:

RQ2. Does the Tips by Text intervention improve Reception children's social development skills?

RQ3. Does the Tips by Text intervention improve literacy outcomes differentially for children eligible for Free School Meals (FSM)?

RQ4. Does the Tips by Text intervention improve literacy outcomes differentially for children with low and high baseline attainment?

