The sample size was determined with the aim of establishing a MDES of 0.1, given the previous research by York and Loeb (2018), which found an impact of the programme on literacy of 0.11 standard deviations. MDES calculations were conducted using Optimal Design software.

All estimates are based on standard EEF assumptions of 80% power and 5% significance level. We assume the pre-test explains 40 per cent of the variation in the post-test scores¹, and that 10 per cent of variance is explained by the blocking variable² (or effectively here, an ICC of 0.10). To achieve an MDES of 0.1 this suggested a required sample size of around 105 schools based on an average of 26 pupils per school (assuming an average of 30 pupils per school, and then allowing for around 5 per cent of pupils to withdraw before randomisation and around 10 per cent of the remainder lost to follow-up). As set out in the trial protocol, if it proved feasible to recruit around 105 schools (and ultimately 109 were recruited), then only 1 class per school receives the assessment that forms the primary outcome for the trial.

Department for Education Statistics for January 2019 show that 15.8 per cent of pupils in primary schools were eligible for and claiming free school meals (Department for Education, 2019). However, schools with above average proportions of pupils eligible for free school meals (FSM) were targeted in recruitment. On the assumption that on average 10 pupils within the reception year of a school will be eligible for FSM, equivalent to around 38 per cent of pupils (at the time of writing the protocol, this was the average percentage of pupils eligible for FSM in recruited schools), and keeping all other assumptions the same, this results in an MDES of 0.14. The trial is not however designed with the aim of detecting an effect for the FSM subgroup as the primary population of interest.

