³ Except in the event of further withdrawals. Pupils who have subsequently left their school will also not be tested.

Analysis

The estimated impact will be based on the difference between those assigned to the treatment and control groups, regardless of contamination of the control group or drop out. This is in order to estimate the "intention-to-treat" (ITT) effect. In addition, the regression models used for the primary analysis will include controls for prior attainment (that is, using the YARC total score as captured at pre-test), as well as a dummy variable to indicate those schools which were randomised in the first batch.

Estimated impact in terms of pupil's outcomes will be converted into a Hedges' g effect size. This will use the estimated total pooled standard deviation of the treatment and control groups, rather than the within-school pooled standard deviation as the former is a more conservative approach.

For each measure, we will estimate outcomes using a linear regression model including a dummy variable indicating trial arm allocation, and school fixed effects. We prefer this approach over multi-level analysis which relies on an assumption that random effects are independent of regressors (Ebbes, 2004).

Primary outcome analysis

The primary outcome to be assessed in this trial is literacy, as measured by the York Assessment of Reading for Comprehension (YARC). The version of the YARC suitable for 4-7 year olds is called Early Reading and covers four dimensions: sound isolation, sound deletion, letter sound knowledge, and early word recognition. To reduce testing time and burden on the school, only the former two measures were used as a pre-test as they are considered the most sensitive and more appropriate for the younger age of the children by GL Assessment and then all four dimensions are to be used at post-test. The primary outcome will be a "total" YARC score, where we will standardise each of the components to have a mean of zero and standard deviation of one. These will then be added together to create a composite measure and re-standardised (calculated where all four components are non-missing). We propose this approach, rather than simply summing together the four scales, given the subscales are not of equal length and thus a simple sum would give greater weight to the longer subscales. The same approach will be adopted with the two subscales used for the pre-test.

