More precisely, our outcome measure will be the total difficulties score from the SDQ. This is a standard SDQ measure which is constructed from summing together responses on four of the five SDQ subscales, giving a score which ranges from 0 to 40. Following existing conventions in using the SDQ (Vaz et al., 2016), if at least three of the five items within a subscale are completed, any remaining missing scores will be replaced by the mean for that subscale. If fewer than three items are completed, no score will be computed for that subscale, and if any of the four subscales are missing, the total difficulties score will not be computed. The extent of missingness in these data, including by treatment and control arm, will be presented in the report. We will also run separate models for three components; 'internalising problems' (which combines the emotional symptoms and peer relationship problems scales, 10 items), 'externalising problems' (which combines the conduct problems and hyperactivity scales, 10 items) and the prosocial scale (5 items). This division of the scales has been shown to be more appropriate for low-risk or general population samples (Goodman et al., 2010).

Subgroup analyses

We will conduct separate analysis of the subgroup of pupils eligible for Free School Meals. Pupils eligible for FSM will be identified using the variable EVERFSM_6_P available from the NPD. This analysis will be conducted for both the primary and secondary outcome; all other subgroup and additional analyses will be conducted only for the primary outcome.

We will run analyses interacting treatment allocation with FSM status, as well as running separate models for the FSM and non-FSM subgroups. The same specification will be used as for the primary analysis. The effect size for FSM pupils will be presented on the basis of the subgroup model, as per the EEF statistical analysis guidance.

Given existing research has suggested differences in impact according to prior attainment (e.g. York and Loeb, 2018), as specified in the trial protocol, we will also conduct a separate subgroup analysis for "high" and "low" attaining pupils, based on the pre-test assessments. These groups will be defined by dividing the sample in half, based on the median score on the

⁴ Further details of the reasons for missingness will be presented in the evaluation report.

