pre-test, which follows the approach adopted by York and Loeb (2018). Again we will report results both using interaction effects and as separate subgroups. The same model specification will be used as for the primary analysis.

Additional analyses

At the time of preparing this SAP, it is unclear whether some testing may need to happen remotely, rather than in person, as a result of Covid-19 restrictions. If remote testing is used, we will run an additional model for our primary analysis that also includes a dummy variable that captures whether the assessment was conducted remotely or not (i.e. in order to check for mode effects). We will also explore the sensitivity of the results to running a model which excludes any pupils for whom the post-tests were conducted remotely. Another potential implication of Covid-19 is that it may prove necessary to extend the post-testing period. The main post-testing period is November-December 2020; if this extends into January 2021, we will run an additional model that includes a dummy variable for any assessments conducted in January, to assess whether there are any implications for the results of the extended testing period.

We will also run an additional model for the primary analysis that additionally includes school by treatment interaction effects as well as school effects. The inclusion of interaction effects allows for the possibility that the effect of the intervention varies across schools (Singh et al., 2019), and so it is useful to check the robustness of our main results allowing for this.

We will also run a model that excludes pre-test scores and simply regresses post-test scores on treatment indicator and randomisation batch, to assess the sensitivity of results to the inclusion of the pre-test. This is of particular relevance given the fact that there are indications of floor effects in the pre-test data, even though the subscales used at pre-test are intended to be suitable for this age group based on guidance from the test provider. We will also run the model restricting to the sample for which pre-test scores are available (i.e. without imputing pre-test scores where these are missing).

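### RQ4 is examined only through groups formed at the pre-test median; adding a treatment-by-continuous-pre-test interaction would be a cheap gain in information

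*SAP*

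**What the plan says.** The Introduction lists RQ4 among the secondary questions: "Does the Tips by Text intervention improve literacy outcomes differentially for children with low and high baseline attainment".

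Subgroup analyses defines the groups: "These groups will be defined by dividing the sample in half, based on the median score on the" pre-test. The SAP says that the subgroup analysis is specified in the protocol and that the split follows the earlier study of the programme. It continues: "Again we will report results both using interaction effects and as separate subgroups". The word Again points back to the free school meals (FSM) paragraph: "We will run analyses interacting treatment allocation with FSM status, as well as running separate models for the FSM and non-FSM subgroups". Read in parallel, the RQ4 interaction is treatment by high/low group. No treatment-by-continuous-pre-test term appears anywhere in the SAP.

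The pre-test is a numeric score. Under Primary outcome analysis, the post-test components are standardised, added and re-standardised, and "The same approach will be adopted with the two subscales used for the pre-test". That score is a covariate in the primary model, whose specification also applies to RQ4. Additional analyses reports that "there are indications of floor effects in the pre-test data", but gives no floor share, and no rule for ties at the median is stated. Update v1.1 says that post-testing stopped with about a third of the expected assessments; it does not change the RQ4 analysis.

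**The concern.** Cutting a numeric moderator at its median fixes the treatment effect as constant within each half, so differences in effect among pupils in the same half do not contribute to the test. The full score is available and already modelled, so this loss of information is avoidable. It matters more now that only about a third of the post-tests were completed.

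Floor scores are tied scores. If ties reached the median, group membership would depend on an assignment rule that the SAP does not give. The SAP responds to the floor effect with a sensitivity model for the primary analysis, but does not carry it through to the subgroup definition. Following the earlier study is a good reason to show the split. It is a weaker reason to have nothing beside it.

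**Working it through.** **Inputs from the SAP (Sample size calculations overview).** "All estimates are based on standard EEF assumptions of 80% power and 5% significance level", two-sided, so the multiplier is 1.960 + 0.842 = 2.802. The text has the pre-test explaining 40% of post-test variance and school explaining 10%. Residual share: (1 - 0.40)(1 - 0.10) = 0.54. Allocation is 1:1.

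**Assumptions of mine.** Analysed sample 2,646/3 = 882, from the statement that about a third of the anticipated post-tests were completed. The shape of the pre-test distribution is also assumed, because the SAP does not give it.

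**1. The plan's own figure.** The SAP states no power or detectable difference for RQ4. The nearest figure is the overall MDES of 0.10 (105 schools, 2,730 pupils).
- Stated inputs alone: 2.802 x sqrt(4 x 0.54/2,730) = 0.079.
- Adding an effect variance between schools of 0.05, which the SAP does not state: 2.802 x sqrt(0.05/105 + 2.16/2,730) = 0.100. The same addition gives 0.14 for FSM (1,050 pupils) and 0.11 for 100 schools of 20, as stated.

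So the stated figures are reproduced only with that unstated input. I leave it out below. The loss in step 2 depends only on the score distribution and the shape of the moderation.

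**2. Information lost by the split.** If the effect is linear in the score, the relative efficiency of the split is the squared correlation between score and group indicator. For a normal score this is 2/pi = 0.637, a loss of 36%. Equal precision then needs pi/2 = 1.57 times the pupils. Where the continuous test has 80% power, the split has 61%.

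For a normal score censored at a floor, the last column divides 0.637 by the squared correlation between underlying and observed score (0.968, 0.923, 0.869, 0.806, 0.733 for floors of 10% to 50%):

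| Pupils at floor | Loss, effect linear in observed score | Loss, effect linear in underlying attainment |
|---|---|---|
| 0% | 36% | 36% |
| 10% | 33% | 34% |
| 20% | 32% | 31% |
| 30% | 35% | 27% |
| 40% | 41% | 21% |
| 50% | 53% | 13% |

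Other assumed observed-score shapes: bounded integer scores with mild skew, about 26-31%; strong right skew, about 36-49%; exponential, 52%. With more than 50% at the floor, the sample cannot be cut into halves.

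**3. Detectable difference at 882 pupils, normal score.**
- SE of the overall effect: sqrt(4 x 0.54/882) = 0.0495.
- Split: SE of the difference between halves is 2 x 0.0495 = 0.099; detectable difference 2.802 x 0.099 = 0.28 SD.
- Continuous: detectable slope 2.802 x 0.0495 = 0.139 per SD of pre-test. The half means lie 2 x sqrt(2/pi) = 1.596 SD apart, so the equivalent is 0.139 x 1.596 = 0.22 SD.

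At the full 2,646 the split detects 0.16 SD and the continuous score 0.080 x 1.596 = 0.13 SD. If only a third of the 2,392 pre-tested pupils contribute (797), the figures are 0.29 and 0.146 x 1.596 = 0.23 SD.

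**4. Power for a modest difference.** Suppose the halves differ by 0.11 SD, the size of the overall effect cited from the earlier study (an illustration only).
- Split: 0.11/0.099 = 1.11, power about 20%.
- Continuous: SE 0.0495 x 1.596 = 0.079; 0.11/0.079 = 1.39, power about 28%.

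**The case against.** The split answers RQ4 as worded, which is a low-versus-high contrast. It is pre-specified, follows the study that motivated the question, and is tested with an interaction as well as separate models. A linear slope is a different quantity, and the loss above is measured against it. If the effect steps near the median, the split need not lose anything. All of this stands, and it is why the split should stay.

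Four stronger readings are tempting, but the SAP does not support them.
- A reader might take a loss of about a third as fact. It is the result for a normal score with linear moderation, or for a modest floor on the observed score. The SAP gives no distribution.
- A reader might infer that the floor makes the split worse. At floors of 10-30% the loss is slightly below the no-floor value. At higher floors the direction depends on whether the effect follows the observed score or underlying attainment. A floor also damages a linear interaction.
- A reader might infer that the sample cannot be halved. That requires a heavy pile-up at the median. The score combines two subscales, so a pupil must be at the floor on both to sit at the composite floor. Histograms of the pre-test are planned (Imbalance at baseline).
- A reader might blame the split for an uninformative null. Step 4 shows that sample size is the main cause, and Update v1.1 acknowledges that limit.

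Nor is the pre-test discarded: it stays in the model as a covariate. Only variation of the treatment effect within each half is ignored.

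**Conclusion.** The point holds as a matter of efficiency for one secondary question. It is not an error or a contradiction, and the primary analysis is untouched. RQ4 is examined only through groups formed at the median, and a more informative analysis of the same data is available.

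Under roughly linear moderation, the loss is 36% for a normal score and roughly a quarter to a half across plausible observed-score distributions. It falls to about 13-21% if underlying attainment is the moderator and the floor is 40-50%, and may be nil for a step near the median. At about 880 pupils the gain is from 0.28 to 0.22 SD in detectable difference, for a normal pre-test and with the SAP's variance assumptions. RQ4 remains low-powered with either method, so a null result should not be read as evidence of a uniform effect. Severity: optional, cheap improvement.

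**What to change.** - Add to Subgroup analyses a treatment-by-continuous-pre-test interaction, with the pre-test main effect and school fixed effects, specified before the RQ4 results are seen. Report the predicted effect with its interval at, for example, the 25th and 75th percentiles of the pre-test.
- Check linearity by adding an at-floor indicator and its interaction with treatment.
- Keep the protocol-specified median split, interaction and separate models, for the low/high contrast and for comparison with the earlier study.
- State how pupils tied at the median are assigned, and report the floor share and the resulting group sizes.
- Record the addition in the version history, as was done for the Bayesian analysis, since it would come after post-testing stopped.

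The cost is one main extra model, its linearity check and a few sentences, with no new data. The downside is the linearity assumption, which the at-floor check and the retained split help to expose.

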The trial protocol identified two additional secondary research questions:

Does the Tips by Text intervention improve Reception children's numeracy outcomes?

 Does the Tips by Text intervention improve Reception children's language and communication outcomes?

However, these two research questions will no longer be explored within the trial, as they relied on data from the Early Years Foundation Stage Profile, which, in line with other national assessments, has no longer been conducted for this cohort of children given the Covid-19 crisis.

Design overview

Please ensure all details are in line with the latest version of the protocol.

Trial design, including number of arms		Two-arm randomised controlled trial		
Unit of randomisation		Parent		
Stratification variables (if applicable)		None		
Primary outcome	variable	Literacy attainment		
	measure (instrument, scale, source)	YARC total score, YARC Early Reading, GL Assessment		
Secondary outcome(s)	variable(s)	Socio-emotional outcomes		
	measure(s) (instrument, scale, source)	Total Difficulties Score, Strengths and Difficulties Questionnaire		
Baseline for	variable	Literacy attainment		
primary outcome	measure (instrument, scale, source)	YARC score (YARC Early Reading sound deletion and sound isolation subscales), GL Assessment		
Baseline for	variable	-		
secondary outcome	measure (instrument, scale, source)	-		

In collaboration with the delivery team, it was agreed that the trial would use individual level randomisation (at the parent level, in order to avoid a scenario whereby twins are assigned to different groups) to reduce the number of schools needed for the trial and to maximise the power to detect an effect. The trial has two arms so that half the eligible children's parents within participating schools were allocated to the treatment arm (receiving the programme) and half to the control arm (who do not receive the programme). All reception classes were randomised, so that for each reception class half were randomly allocated to receive the intervention and half do not. Although we cannot rule out the possibility of contamination of the control group from the sharing of Tips by Text content, it is expected by the delivery team

that the number of parents who speak to each other about the text messages, or directly share the messages with one another, will be limited.

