We will conduct exploratory analysis that examines separately whether there is an impact of the intervention on each of the four YARC subscales administered at post-test: letter sound knowledge, early word recognition, sound isolation, and sound deletion. This will follow the same model specification for the primary outcome, and adjust for the total YARC pre-test score in each case.

Analyses in response to missing data are discussed further below.

Update v1.1: Due to the third national lockdown and associated disruption for schools as a result of Covid-19, the decision was taken to stop post-testing in January 2021. This has resulted in a smaller number of completed post-assessments (around a third of the anticipated number). The smaller than anticipated sample size available for analysis inevitably has implications for the ability of the originally proposed analysis to detect a statistically significant effect (more generally, there is of course wider debate around the use of p-values to judge statistical significance, see for example, the discussion in Nuzzo, 2014). Bayesian methods can be used as an alternative means of evaluating effectiveness and may, though not in all circumstances, offer benefits when working with smaller sample sizes (McNeish, 2016).

While we will carry out the original analysis using frequentist methods as documented in the original version of this SAP, we will also undertake an additional exploratory analysis using a Bayesian approach. This will provide exploratory evidence into the probability that the

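### The four exploratory YARC subscale models adjust only for an equal-weight pre-test total, although its two component scores could be entered separately for a small possible gain in precision

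*SAP*

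**What the plan says.** The subscale models are described under Additional analyses: "We will conduct exploratory analysis that examines separately whether there is an impact of the intervention on each of the four YARC subscales" given at post-test. On their form the SAP says "This will follow the same model specification for the primary outcome", and on the baseline covariate that they "adjust for the total YARC pre-test score in each case".

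The content of that covariate is set elsewhere. The Design overview table gives the baseline measure as "YARC score (YARC Early Reading sound deletion and sound isolation subscales), GL Assessment". Primary outcome analysis lists four dimensions, starting with sound isolation and sound deletion, and says that "only the former two measures were used as a pre-test". The post-test total is built by standardising each component, summing, and standardising again, and only where no component is missing. For the baseline: "The same approach will be adopted with the two subscales used for the pre-test". Every child with a pre-test total therefore has both component scores, and the total weights them equally in standard-deviation units.

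The only reason given for using the total in the subscale models is that they follow the primary specification.

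**The concern.** Sound isolation and sound deletion were each measured before and after with the same instrument. A child's earlier sound-isolation score might well predict later sound isolation better than the earlier sound-deletion score does, and the reverse for sound deletion. The total does not allow this: in each model both scores must carry the same standardised coefficient. If the two predict unequally, some explainable variance stays in the residual and the treatment effect has a wider interval than the collected data allow.

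Only the precision of secondary, exploratory estimates is at stake. For letter sound knowledge and early word recognition there is no same-test baseline, so there is less reason to expect unequal prediction. The same reasoning applies to them if it does occur.

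**Working it through.** The SAP states no figure for these models, so there is none to reproduce. Its one planning value for the pre-test, 40 per cent of post-test variance explained, refers to the total score.

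**Inputs (all assumed; read as within-school correlations, because the model has school fixed effects)**
- *a*: post-test subscale with its own pre-test score
- *b*: post-test subscale with the other pre-test score
- *c*: the two pre-test scores with each other

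**Formulas**
- Equal-weight total: R² = (a + b)² / (2 + 2c)
- Both scores entered separately: R² = (a² + b² − 2abc) / (1 − c²)
- The second minus the first is (a − b)² / (2(1 − c)). This is never negative, and it is zero when a = b.

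The model with the total is the model with two covariates under one constraint, equal standardised coefficients. Freeing the constraint cannot lower R². It costs one degree of freedom, roughly 0.1% of variance at about 880 children (2,646 / 3 = 882, taking the reported third of the anticipated post-tests as a third of 2,646).

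**First case in full (a = 0.60, b = 0.35, c = 0.5)**
- Total: 0.95² / 3 = 0.301
- Separate: (0.36 + 0.1225 − 0.21) / 0.75 = 0.363. Check: 0.25² / (2 × 0.5) = 0.0625, and 0.3008 + 0.0625 = 0.363.
- Residual variance ratio: (1 − 0.363) / (1 − 0.301) = 0.911. Its square root is 0.954, so the standard error falls by 4.6%.

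| a, b, c | R² total | R² separate | Residual variance ratio | Fall in SE |
|---|---|---|---|---|
| 0.60, 0.35, 0.5 | 0.301 | 0.363 | 0.911 | 4.6% |
| 0.50, 0.30, 0.4 | 0.229 | 0.262 | 0.957 | 2.2% |
| 0.50, 0.35, 0.5 | 0.241 | 0.263 | 0.970 | 1.5% |
| 0.45, 0.40, 0.6 | 0.226 | 0.229 | 0.996 | 0.2% |

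**Wider range.** A grid was run over a = 0.40 to 0.63, b = 0.30 to 0.60 (with b not above a) and c = 0.4 to 0.8. In 29 of its 39 combinations, the standard error with the total exceeded that with both scores by 4% or less. In eight the excess was about 5% to 11%. In two extreme ones (c = 0.8, b = 0.30, with a = 0.60 or 0.63) it was 19% and 25%. The large values need two closely related pre-tests that nevertheless predict very differently.

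**Bias.** A simulation used 109 schools of 8 pupils, randomisation within school, school fixed effects, a true effect of 0.10 and 4,000 runs.

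| Baseline covariate | Mean estimate | Empirical SE |
|---|---|---|
| Own pre-test score only | 0.100 | 0.0535 |
| Total | 0.100 | 0.0525 |
| Both, separately | 0.100 | 0.0524 |
| None | 0.100 | 0.0610 |

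No choice of covariate biases the estimate. In this scenario the total performs practically as well as both scores.

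**The case against.** The strongest reply is that this is a choice of covariate form and not an error. The SAP fixes one clearly defined covariate for models it labels exploratory. A common covariate keeps the four models comparable with each other and with the primary analysis. The total already contains each matched score, so no baseline data are discarded. The gain rests on correlations that no document gives, and in the simulated scenario it was nil for practical purposes. Most of this stands and sets the weight of the point. Comparability does not decide it, because the same two covariates would be used in all four models.

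A second reply is that the own-baseline score need not beat the total. That is right for the matched score alone: over the grid, the ratio of standard errors (total to matched) runs from 0.87 to 1.12. The total is better once b/a exceeds √(2(1 + c)) − 1, which is 0.67, 0.79 and 0.90 for c = 0.4, 0.6 and 0.8. This tells against swapping the total for the matched score. It does not tell against entering both.

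A third reply is the handling of missing data. Of the 2,646 pupils, 2,646 − 2,392 = 254 had no pre-test, and the SAP imputes missing pre-test scores in the primary specification. Two scores would then need imputing where one did before. This is a real, small cost.

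Four stronger readings may tempt a reader, and the SAP does not support them:
- *The subscale effects are biased.* Allocation was random within classes, so each choice of covariate is unbiased.
- *Chance imbalance is a further harm beside lost precision.* Over repeated randomisation, imbalance left unadjusted is part of the standard error. The two are one cost.
- *Floor effects make equal weights worse.* The SAP says "there are indications of floor effects in the pre-test data" but does not say that they differ between the subscales. A floor could equally make one score a weak predictor and favour pooling.
- *The loss of post-tests makes this urgent.* Apart from the degree of freedom, the percentage gain does not depend on sample size, and a gain of this order cannot restore power.

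**Conclusion.** The point holds as a minor one. The plan constrains two available pre-test scores to equal weight in all four subscale models, and two of those outcomes have a same-test baseline. The likely price is about 0% to 5% in standard error (0% to 9% in residual variance), and it may be close to zero. It is larger only if the two scores predict a subscale very unequally while being strongly correlated with each other. These sizes rest wholly on assumed correlations; the direction rests only on one model containing the other, less one degree of freedom. The primary analysis is untouched, and no confirmatory conclusion depends on the subscale models.

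**What to change.** In the SAP's paragraph on the four subscale models, replace adjustment for the pre-test total by adjustment for the standardised sound-isolation and sound-deletion pre-test scores, entered as two separate covariates in each model. State that where the pre-test is missing both scores are imputed under the existing Missing data rules. Keep the treatment indicator, batch indicator and school fixed effects as they are, and leave the primary model unchanged. If the team prefers to keep the total for consistency with the primary model, the two-covariate version can be reported as a sensitivity analysis.

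The cost is a change of wording, one extra coefficient per model and one extra variable to impute. No new data are needed, and no child who has a pre-test total is lost.
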